Aim 2. Determine the influence of typical alcohol use and expectation of pain relief with alcohol use on magnitude of alcohol analgesia and associated feelings of relief. Studies of alcohol analgesia in healthy adults have indicated that individual patterns of typical alcohol use, motivation to drink, and personality factors may modulate alcohol analgesia, suggesting a critical role of conditioning and expectancies (Brown and Cutter, 1977; Cutter et al., 1979; Ralevski et al., 2010). However, this question has never been directly examined, either in healthy adults or those with chronic pain. **H4.** We predict individuals with stronger positive expectancies regarding alcohol analgesia will have significantly stronger analgesic responses to alcohol administration. **H5.** Based on previous research, we predict that individuals who endorse greater and more frequent alcohol consumption will experience a greater analgesic effect of alcohol, independent of the effect of expectancies. Finally, we ask as **E2.** whether chronic pain status will be associated with stronger expectancies of pain relief following alcohol consumption and **E3.** greater ratings of pain relief during pressure algometry after drinking.

6. Research Plan:

General Approach. For this study of current non-problem drinkers, we propose a repeated-measures, double blind placebo-controlled factorial design with chronic pain status (TMD vs. healthy control) as a between-subjects factor and alcohol administration (Alcohol Dose: placebo, 0.08 g/dL) as a within-subjects factor. The study will include both men and women. Study procedures will occur at the Center for Pain Research and Behavioral Health of the University of Florida under supervision of the PI (JB).

Methods

Participants. Individuals seeking care for temporomandibular joint and muscle disorder (TMD) (n=25) will be recruited for the study via flyers, word of mouth, internet/local radio advertisements, and [name] orthodontic clinic. A sample of healthy social drinkers without TMD (HC) will also be recruited as a comparison group (n=25). Individuals aged 21-45 years will be recruited to avoid any vulnerability to acute neurobehavioral effects of alcohol associated with older age (e.g., [name] et al., 2016a). Because TMD is more prevalent in women than men (~2:1; Campbell et al., 2017), we anticipate the final sample will consist of approximately 2/3 women.

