
Alcohol Administration. Alcohol administration procedures are consistent with our previous work and NIAAA guidelines for the safe and ethical administration of alcohol in

experimental settings (Brown et al., 2014). Participants will complete two laboratory sessions in which they will be administered one of two beverages: placebo (0.00 g/dL target BrAC) or active alcohol (0.08 g/dL target BrAC). Session order will be counterbalanced across participants. For laboratory sessions in which a participant will be given the active dose, the quantity of medical/United States Pharmacopeia grade alcohol (100% or 95% ethanol) needed to achieve 0.08 g/dL (i.e., approximately 3-4 standard drinks) will be calculated using a modification of the Widmark formula. This formula utilizes age and weight measures for men and height and weight measures for women (Watson, et al., 1981; Widmark, 1932). For example, a 30-year old man who is 183 cm tall and weighs 75 kg would receive 55.3 ml of absolute ethanol, or ~.58 g/kg. In order to maintain the study's double blind, a researcher not involved in QST will be responsible for calculating alcohol doses and mixing drinks, and the dose calculation and mixing procedure confirmed by a second research assistant. Pre-calculated dose lookup tables indexing height and weight for women and age and weight for men will be used to avoid dosing errors. Alcohol will be mixed with cold sugar-free lemon-lime soda in a 1:3 ratio and split into two servings ([name], et al., 2014; Gilbertson, et al., 2009; Harrison et al., 2007). Placebo beverages will consist of only soda. Participants will consume both servings within 5 minutes. **Both active and placebo drinks will be misted with alcohol to enhance placebo effectiveness. A small amount of alcohol will be placed on the rim of the glass and floated on the surface of the beverage to further mask the study condition.** Participants will rinse their mouths thoroughly with water once their beverage has been consumed. No suggestion regarding the potential pain-relieving effects of alcohol will be provided before or after beverage administration to avoid influencing expectations. All study staff over the age of 21 designated as "Interacts or intervenes directly with study subjects" on the myIRB smart form will be trained by the PI how to use the lookup tables and mix beverages and may serve in this capacity depending on availability for a given laboratory session.

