
Data Analysis Strategy. Data will be analyzed using SPSS 24 (IBM Corp., Armonk, NY).

Aim 1. Determine the effect of chronic pain status on magnitude of alcohol analgesia and associated feelings of relief. To assess hypotheses and empirical questions related to Aim 1, chronic pain status will be included as an independent variable in repeated measures general linear models analyses (rmGLM; SPSS GLM procedure; repeated: dose), with QST measures, associated relief ratings, and SEAS measures as dependent variables. Demographic, personality/affective (i.e., BDI/STAI/IRQ/BFI), substance use-related (recent alcohol use/alcohol use disorder symptomatology), pain-related (TMD severity), and biological (i.e., approximated menstrual phase for female participants) variables will be included as covariates should any correlate significantly with magnitude of alcohol analgesia or relief ratings.

Aim 2. Determine the influence of typical alcohol use, and alcohol analgesia-related expectancies on magnitude of alcohol analgesia and associated feelings of relief. A combination of approaches will be used to address Aim 2. Simultaneous multiple regression of alcohol analgesia expectancy and typical alcohol consumption

(estimated in ounces of absolute ethanol consumed per day derived from the AUQ) on QST measures will be used to evaluate H4 and H5. As in Aim 1, rmGLM will be used to assess E2 and E3.

Power Analysis. Power analyses for the proposed work are based on effect sizes derived from our initial feasibility study (see attached grant application for details) and were performed assuming two-tailed hypothesis tests with alpha=.05. Effect sizes are reported as Cohen's d, Pearson's r, or R2 (Cohen, 1988). Analyses indicated N=50 would provide excellent (98%) power to detect analgesic effects of alcohol administration on QST measures (Cohen's d > .58) and correlations between VAS ratings of relief and alcohol analgesia (r = .64). Critically, this sample size will also provide 80% power to detect small-to-medium sized effects (d > .40; r > .37; R² > .14) for which prior estimates are not available (e.g., the effect of chronic pain status on alcohol analgesia and subject alcohol affects). *We will recruit a total of 60 qualified subjects over the course of the project to account for 10% anticipated participant dropout before completing all study visits.*

7. Possible Discomforts and Risks:

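### Healthy controls have no sex matching or quota, so the two-thirds-women forecast follows only for the TMD group, and sex is adjusted for in the TMD-versus-control comparisons only if it passes a significance screen

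*Combined protocol and SAP*

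**What the plan says.** Section 6 (Participants) sets up the two groups separately. For TMD: "Individuals seeking care for temporomandibular joint and muscle disorder (TMD) (n=25) will be recruited". For controls: "A sample of healthy social drinkers without TMD (HC) will also be recruited as a comparison group (n=25"). Both sexes are eligible ("The study will include both men and women"), and one age range applies to everyone ("Individuals aged 21-45 years will be recruited"). Neither that section nor Selection Criteria or Screening Procedure gives a matching rule, stratum or quota by sex.

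The forecast for the whole sample is "we anticipate the final sample will consist of approximately 2/3 women". Its stated reason is "Because TMD is more prevalent in women than men (~2:1").

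Section 6 (Data Analysis Strategy, Aim 1) lists candidate covariates, demographic variables among them, which "will be included as covariates should any correlate significantly with magnitude of alcohol analgesia or relief ratings". Sex is not named as a fixed term. For Aim 2, E2 and E3 are to be assessed with the same type of model as in Aim 1.

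**The concern.** The 2:1 ratio describes people with TMD. It supports two-thirds women in the TMD group, but it gives no information about healthy drinkers recruited through a separate stream. The forecast for both groups together therefore needs controls who are also about two-thirds women, and nothing in the plan brings that about.

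This matters because chronic pain status is not randomised. H3 and E1 (whether pain status changes the size of alcohol analgesia) and E2 and E3 (expectancies and relief by pain status) are observational comparisons of 25 with 25. Their comparability rests on recruitment and on the model. If the groups differ in sex, and sex is related to the outcome, part of a sex difference can appear as an effect of pain status or can mask one. The planned protection responds to a significant correlation with analgesia or relief, not to imbalance between the groups.

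**Working it through.** **Inputs.** From section 6: 25 per group; about 2/3 women among people with TMD; about 2/3 women forecast overall; two-sided alpha of 0.05. The documents do not give the share of women among controls (*p*) or the sex difference in the alcohol-minus-placebo change score (*d*, in SD units). Both are assumed: *p* from 33% to 60%, *d* of 0.3, 0.5 and 0.8.

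**1. The forecast.** Women = 25 × 2/3 + 25 × *p*.

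- *p* = 2/3: 16.7 + 16.7 = 33.3 of 50, or 67%. This reproduces the plan's figure.
- *p* = 60%: 16.7 + 15.0 = 31.7, or 63%.
- *p* = 50%: 16.7 + 12.5 = 29.2, or 58%.
- *p* = 40%: 16.7 + 10.0 = 26.7, or 53%.

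With half the controls women, the TMD group would have to be 2 × 2/3 − 1/2 = 83% women to reach 2/3 overall.

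**2. Imbalance.** With binomial sampling, 25 per group, TMD at 2/3 and controls at 1/2, the chance that the TMD group has at least 5 more women is 46%. Even if both pools are 2/3 women, a gap of 5 or more in either direction has an 18% chance.

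**3. Bias in H3 with no adjustment.** Bias = (2/3 − *p*) × *d*. For example, 0.167 × 0.5 = 0.08 SD, and 0.333 × 0.5 = 0.17 SD.

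**4. Bias in H3 under the planned rule.** Trials of 25 per group were simulated with no true group effect, adding sex only if its correlation with the change score had p < 0.05. There were 20,000 runs per row, or 6,000 for the 33% rows.

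| Controls women | *d* | Sex enters | Bias, no adjustment | Bias, plan's rule | Type I, no adjustment | Type I, plan's rule |
|---|---|---|---|---|---|---|
| 50% | 0.3 | 17% | 0.05 | 0.03 | 5.2% | 4.8% |
| 50% | 0.5 | 39% | 0.08 | 0.03 | 5.9% | 5.3% |
| 50% | 0.8 | 77% | 0.13 | 0.02 | 7.3% | 5.2% |
| 40% | 0.5 | 40% | 0.13 | 0.05 | 7.3% | 5.1% |
| 40% | 0.8 | 79% | 0.21 | 0.02 | 10.8% | 5.2% |
| 33% | 0.5 | about 40% | 0.17 | 0.06 | 8.5% | 5.0% |
| 33% | 0.8 | about 78% | 0.27 | 0.02 | 12.9% | 5.2% |

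Across all runs with controls at 33% to 50% women, the rule left an average bias of about 0.02 to 0.07 SD and a type I error of about 4.7% to 5.7%. In the trials where sex was not entered, the bias was about 0.03 to 0.13 SD; a repeat run put the most extreme cell (33%, *d* = 0.8) at 0.14. For scale, the standard error of a 25-versus-25 difference is √(2/25) = 0.28 SD, so an average bias of 0.07 is a quarter of it.

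**5. Always including sex.** The bias was zero within simulation error and type I error about 5% in every scenario.

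**6. E2.** The trigger names analgesia and relief. A sex difference in expectancies alone would not set it off, so the no-adjustment columns are nearer to what E2 faces. How near depends on sex differences that the documents do not give.

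**The case against.** The best defence is that the plan already screens the right quantity. Confounding by sex needs both an imbalance and an association with the outcome, and the rule tests the association. It misses mostly when the observed sex effect is small, and then the bias is small too. The simulation bears this out for H3, and that part stands.

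Four stronger readings are tempting, and the documents do not support them.

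- **Inflated type I error.** A reader might infer false-positive rates for H3 of roughly 6% to 15%. Those belong to a test with no adjustment, which is not the planned analysis for H3.
- **Unequal dosing.** A reader might take the sex-specific dose inputs ("This formula utilizes age and weight measures for men and height and weight measures for women") as a second route to confounding. Both calculations aim at the same target BrAC, so this is not evidence of unequal exposure. Menstrual phase is already a candidate covariate.
- **Age.** A reader might extend the point to age. Both groups share the 21-45 limit, age falls under the demographic covariates, and no age effect has been shown.
- **An error in the plan.** The 2/3 figure is a forecast. It feeds no calculation, the power analysis included, and it is compatible with an unstated intention to recruit similar controls.

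It is also fair to say that the study is meant partly to supply feasibility and effect-size data, and that both drivers of harm are assumed here.

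**Conclusion.** The point holds in a modest form. The forecast follows from the stated reason for the TMD group only; with half the controls women it would be 58% overall. Sex may differ between the groups in H3, E1, E2 and E3, and the planned adjustment would leave sex out in about 8 of 10 trials at a 0.3 SD sex difference and 6 of 10 at 0.5 SD.

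For H3 the consequence is small: about 0.02 to 0.07 SD of bias on average, with type I error near 5%. The cost is mainly to interpretation. When sex is unbalanced and not in the model, a reader cannot separate it from pain status. E2 is least protected. H1 and H2 are within-subject contrasts and are untouched.

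These sizes rest on assumed values for the controls' share of women (33% to 50%) and for the sex difference (0.3 to 0.8 SD).

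**What to change.** 1. In Data Analysis Strategy, name sex as a prespecified term in all TMD-versus-control models (H3, E1, E2, E3), kept whatever its p-value. Sex must already be known to calculate the dose, so nothing new is collected. The cost is one degree of freedom.
2. In Participants, frequency-match control recruitment to the TMD group on sex. The 2/3 forecast then follows for both groups (33.3 of 50), and the expected sex bias is zero; the fixed term deals with chance imbalance. The cost is a recruitment-log rule, some surplus control volunteers not enrolled, and control recruitment running slightly behind TMD recruitment.
3. If matching is not wanted, restate the forecast as applying to the TMD group only.

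Matching on age bands as well is optional. Reporting sex by group would let readers judge comparability under any of these choices.

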Table 1. Screening Measures. BDI-II: Beck Depression Inventory (Beck et al., 1996); STAI: State-Trait Anxiety Inventory (Spielberger, 1983); AEQ: Alcohol Expectancies Questionnaire (Brown et al., 1987); AUQ: Alcohol Use Questionnaire (Cahalan et al., 1969); AUDIT: Alcohol Use Disorders Identification Test (Saunders et al., 1993); PILL: Pennebaker Inventory of Limbic Languidness; FTQ: Family Tree Questionnaire (Mann et al., 1985); PSQI: *Pittsburgh Sleep Quality Index* (Buysse et al., 1989). BRS: Brief Resilience Scale (Smith et al., 2008); DIS: Discomfort Intolerance Scale (Schmidt et al., 2006); EAA: Expectancies for Alcohol Analgesia Inventory (Ditre et al., 2018); PCS: Pain Catastrophizing Scale (Sullivan et al., 1995); PASS-20: Pain Anxiety Symptoms Scale (Short Version; McCracken and Dhinra, 2002); IRI: Interpersonal Reactivity Inventory (Davis, 1980), OHIP-TMD: Oral Health Impact Profile for TMDs (Durham et al., 2011).

Screening Procedure. Interested individuals contacting the Center for Pain Research and Behavioral Health via phone or email will be scheduled for a formal screening session. [name] will also facilitate contact between potential TMD participants he encounters as a part of his orofacial pain practice and study staff. During screening, information regarding demographics, FH of drug and alcohol use (including nicotine),

typical drinking behavior, affective and personality, alcohol-related expectancies, and medical history will be collected (see Table 1). The PI will facilitate contact with clinical services if desired. Subjects endorsing suicidal intent will be withdrawn from the study. [name], a licensed clinical psychologist, will provide an appropriate referral. Baseline quantitative sensory testing (QST) measures of pain sensitivity and tolerance using pressure algometry at the insertion of the masseter muscle (described in detail below) will be taken after participants' eligibility and willingness to continue is confirmed. Participants will provide their own transportation to screening sessions. Participants will be paid \$15 for completing screening, requiring ~1-2 hours.

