Laboratory Sessions. Consistent with previous work ([name], et al., 2014; Lewis, et al., 2013), participants will be asked to fast for at least 4 hours prior to their scheduled session and abstain from alcohol consumption 24 hours before each of the two laboratory sessions. Use of non-steroidal anti-inflammatory drugs (NSAIDs) in the 12 hours prior to testing will also be restricted. Normal morning medications will be permitted, but OTC medications (including allergy medications and analgesics) will not be allowed. **A urine- based drug screen for tetrahydrocannabinol, cocaine, benzodiazepines, morphine, and methamphetamine (Innovacon, Inc., San Diego, CA) will be performed. Participants testing positive for any substance will be discontinued. A baseline breath alcohol concentration (BrAC) measure will be taken, which must be negative.** Women will complete a brief questionnaire regarding their menstrual cycle, including: 1) if they are currently menstruating or post-menopausal; 2) typical time between menstruation; 3) days elapsed since last menses; 4) typical menses length; and 5) use of any hormonal preparations (e.g., birth control). **Women of child bearing potential will be given a pregnancy test; positive tests will result in exclusion from the study with a recommendation to contact her physician.** Women who are currently breastfeeding will also be discontinued. All testing will be conducted in private rooms within the Center for Pain Research and Behavioral Health. Participants will be provided with a light breakfast one hour before alcohol administration (~200 kcal). Following breakfast, participants will repeat affective measures (BDI-II/STAI) as well as an Irritability Questionnaire (IRQ; Craig et al., 2008). Lunch will be provided following testing, as well as another light meal as needed. At the conclusion of their final laboratory session, individuals in the TMD group will also be asked whether and how frequently (never, sometimes, frequently, always) they have used alcohol to help control their TMD pain (Riley and King, 2009). For laboratory sessions, the PI or a research assistant will schedule a ride with Uber or Lyft to drive participants home after the completion of the session. Research assistants will use the GPS features of the rideshare app to ensure that participants make it home safely. If the rideshare app indicates that the participant was dropped off somewhere other than the vicinity of their home, the attending researcher will call the number left by the participant and speak with the participant. If the participant does not answer the phone, the researcher will contact the IRB to report the protocol deviation. Participants will be paid \$50 for completing each of the two laboratory sessions. Laboratory sessions will be separated by at least 48 hours.

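### Session order is counterbalanced but left out of the Aim 1 repeated-measures model, so any shift between the two sessions is counted as error and weakens the dose test

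*Combined protocol and SAP*

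**What the plan says.** The General Approach paragraph of the Research Plan treats "alcohol administration (Alcohol Dose: placebo, 0.08 g/dL) as a within-subjects factor", with chronic pain status between subjects. Under Alcohol Administration, "Session order will be counterbalanced across participants". It does not say whether this holds within the TMD and control groups or only overall. Under Laboratory Sessions, "Laboratory sessions will be separated by at least 48 hours".

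For Aim 1, the Data Analysis Strategy specifies "repeated measures general linear models analyses (rmGLM; SPSS GLM procedure; repeated: dose"), with chronic pain status as the independent variable. The candidate covariates are demographic, personality/affective, substance-use, pain-related and biological. These "variables will be included as covariates should any correlate significantly with magnitude of alcohol analgesia or relief ratings". Session order, session number and period appear nowhere in the analysis strategy, in either Aim 1 or Aim 2.

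**The concern.** This is a two-period crossover. Suppose ratings drift between sessions through habituation, sensitisation or a change in how the scale is used. A participant who has alcohol second then has that drift added to the alcohol–placebo difference, and one who has alcohol first has it subtracted. Counterbalancing makes the two cancel in the overall mean. It does not remove the spread they create between participants, and a model without order treats that spread as noise.

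The dose tests behind H1 and H2 would then lose power and become conservative, although order is known for everyone. For H3/E1, the group-by-dose contrast picks up part of the drift if one group has more alcohol-first participants than the other. The covariate rule does not help: order is not a listed candidate, and entry depends on a significance screen.

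**Working it through.** **Inputs from the plan.** 25 TMD and 25 control participants (Participants). Power calculations were "performed assuming two-tailed hypothesis tests with alpha=.05" (Power Analysis). "Analyses indicated N=50 would provide excellent (98%) power to detect analgesic effects of alcohol administration on QST measures (Cohen's d > .58"). The same section claims 80% power for d > .40.

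**The plan's own figures.** A within-person test with N = 50 has noncentrality d√50 and, with one group factor, 48 error df.
- d = .58: noncentrality 4.101, power 98.0% (plan: 98%).
- d = .40: noncentrality 2.828, power 79.1% (plan: 80%).

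Both reproduce as paired tests with no session effect.

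**Assumed quantity.** Let π be the session 2 minus session 1 shift, in SDs of the alcohol–placebo difference. The documents give no value, so .25 to 1.0 is shown.

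**Model.** With two dose levels, the repeated-measures model is equivalent to a regression on each person's difference D:

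D = τ + δ·g/2 + π·o + e, where g = ±1 for group, o = ±1 for order, and e has variance 1.

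Leaving o out raises the residual variance from 1 to about 1 + π². With balanced order, the sampling variance of the mean difference stays at 1/50. The test therefore behaves as if its critical value, 2.011, were multiplied by √(1 + π²). For π = .5 that is 2.011 × 1.118 = 2.248, giving approximate power at d = .40 of Φ(2.828 − 2.248) = Φ(0.580) = 71.9%.

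**Simulation of the dose test** (100,000 replicates per cell; order 13/12 in one group and 12/13 in the other):

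| π | Power, d = .40, no order | Power, d = .58, no order | Type I error, no order |
|---|---|---|---|
| 0 | 79.1% | 98.0% | 5.0% |
| .25 | 77.4% | 97.7% | 4.3% |
| .50 | 71.7% | 96.5% | 2.9% |
| .75 | 61.8% | 93.8% | 1.4% |
| 1.00 | 48.8% | 88.6% | 0.6% |

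With order in the model, power is about 79% and 98% in every row and type I error is about 5%.

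**Group-by-dose test.** If a TMD and b control participants have o = +1, the bias in this contrast is π × 2(a − b)/25. A 14/11 v 11/14 split gives 2 × 3/25 = 0.24π, and a 15/10 v 10/15 split gives 2 × 5/25 = 0.40π. Type I error without order at π = .25, .5, .75, 1.0:
- 14/11 v 11/14: 4.9%, 4.3%, 3.4%, 2.6% (no inflation).
- 15/10 v 10/15: 5.6%, 7.0%, 8.1%, 8.4%.

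If only overall 25/25 balance is enforced and order falls at random with respect to group, a is hypergeometric (50, 25, 25). The chance of a 15/10 v 10/15 split or worse is then 25.8%. Averaged over all such splits, type I error is about 5.0%. With order in the model it is about 5% for every split.

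**The case against.** The omission and the arithmetic are not in dispute; the argument is about importance.

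- **Effect size.** The plan attaches d = .58, not .40, to the alcohol effect on QST measures. At d = .58 a shift of .5 costs only about 1.5 points. This stands for H1. The d = .40 figures apply to a dose effect of that size, for example on relief ratings (H2), for which the plan states no d.
- **No evidence of a large shift.** The protocol takes "Baseline quantitative sensory testing (QST) measures of pain sensitivity and tolerance using pressure algometry at the insertion of the masseter muscle" at screening, marks the site in ink, trains operators and averages three repeats. These features make a first-exposure effect less likely. They do not exclude a shift between two sessions that may be only 48 hours apart, but π of .75 to 1.0 has no support in the documents.
- **Feasibility SD.** The SD behind d = .58 comes from an attachment that is not in these documents. If it already includes session variance, the stated 98% already reflects the loss, and adding order would raise power rather than restore it.
- **Validity.** Under near-balanced order the dose tests do not exceed 5% type I error, and the group-by-dose test averages about 5%. Inflation needs both a shift and an uneven split.

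All four limit the size of the problem. None gives a reason to leave out a design factor that costs almost nothing to include.

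**Conclusion.** The concern holds, conditionally on a session shift. The plan counterbalances order and then leaves it out of the model. The consequence is lost precision, not a biased dose estimate: under 2 points of power at π = .25, and at π = .5 about 7 points for d = .40 or 1.5 points for d = .58. These figures assume 50 completers, near-balanced order and an SD behind d that excludes session variance. The group-by-dose test is at risk only in a realised sample with materially unequal order splits, which the text neither causes nor prevents. The change should be made because its cost is negligible and the possible loss is not.

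**What to change.** 1. In the Data Analysis Strategy, add session order (alcohol first or placebo first) as a between-subjects factor in every repeated-measures model with dose as the repeated factor, for Aim 1 and for E3. The dose-by-order term then absorbs a common session shift. Include it regardless of any correlation screen.
2. Under Alcohol Administration, state that order is counterbalanced separately within the TMD and control groups. Assuming the 60 recruits are 30 per group, allocated 15/15, with 5 lost at random from each, the chance that the alcohol-first counts differ by 5 or more between groups falls from 25.8% to 0.1%.

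**Cost.** One error df, or two if the SPSS default full factorial also adds group-by-order. With no session effect, power at d = .40 is 79.1% without order, 79.1% with it and 79.0% with the full factorial. In the documents it means one line in the analysis plan and two order lists.

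**Limit.** This does not deal with carryover or unblinding that affects only one sequence. A shift c confined to one sequence still moves the order-adjusted dose estimate by c/2; for example, c = .5 moves it by .25.
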